D.1.1. Participants: We will recruit a total of 268 adult participants with cLBP with the expectation of approximately 10% attrition based upon the preliminary work of Drs. [name] and [name]. This will result in a final sample size of 240 (120 non-Hispanic Black, 120 non-Hispanic White) study completers. Participants between 19 and 85 years of age will be enrolled. Enrollment will begin almost immediately after funding is awarded because most of the study policies and procedures have already been established as part of the pilot work previously completed by the PI. The inclusion criteria for participants with cLBP are: 1) non-specific cLBP that has persisted for at least 3 months and has resulted in pain on at least half the days in the past 6 months; 2) age 19 – 85; the lower end of this age range was chosen in order to capture the growing prevalence of young adults with cLBP, and participants over 85 years are increasingly likely to meet one or more exclusion criteria; and 3) participants report ethnic group as non-Hispanic and racial group as either Black/African American or White/Caucasian. Participants with cLBP will be excluded if they have any concurrent medical conditions that could confound interpretation of outcome measures or coexisting disease that could preclude successful completion of the protocol (specific exclusion criteria are presented in the Protection of Human Subjects section).

Given that participants will be primarily recruited from a pain treatment clinic, it is reasonable to assume that many may be using daily opioid medications. We will not exclude participants using opioids daily as this could seriously hinder recruitment efforts or otherwise bias our sampling (e.g., only participants with low severity cLBP not receiving opioids). We are aware that both continued use and temporary withdrawal from these medications (should we ask participants to withhold) could affect pain perception. Therefore, participants will not be asked to withhold pain medications on the day of quantitative sensory testing. Rather, all medications currently being used for pain (e.g., opioids, NSAIDs, SSRIs, etc.) will be recorded and controlled in statistical analyses as needed.

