D.2.1. Clinical pain assessment: The **Patient-Reported Outcomes Measurement Information System (PROMIS)** pain intensity, pain interference, and pain behavior items will be used for this study.¹¹⁰⁻¹¹² For instance, patients will be asked to rate the intensity of their cLBP at its "worst" and "on average" over the past 7 days as well as the intensity "right now". The **Graded Chronic Pain Scale (GCPS)** is a reliable (Cronbach's alpha ≥ 0.80) and well-validated measure that evaluates global pain severity and pain-related interference over the past 6 months.¹¹³ The GCPS yields a "Characteristic Pain Intensity" score and an overall "Disability" score. Taken together, the PROMIS pain intensity items and the GCPS will be our primary clinical outcome measures for data analytic purposes. The **Oswestry Low Back Pain Disability Inventory (ODI)** is a low back-specific instrument designed to address perceived disability in 10 areas: pain intensity, ability to lift objects, walking ability, sitting ability, standing ability, sleep, sex life, social life, traveling, and personal hygiene activities.¹¹⁴

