D.5.1. Follow-up component – predicting pain in daily life: As a component of Specific Aim 3 and to translate the laboratory findings to participants’ daily environment, all participants will be contacted by phone once per week for four weeks following completion of study session 2. Participants will be asked to report on symptoms of pain (average and worst intensity), mood, sleep, disability, and interference of pain with daily activities over the preceding week using appropriate PROMIS items banks.¹¹¹ We have successfully used a similar approach in a previous project to collect weekly follow up data.⁹² Given that racial group differences in follow up data could be attributed to differences in treatments received or in comorbidities since completion of the experimental sessions, we will collect this information and control for these factors statistically, if needed.

D.6. Statistical methods

D.6.1. Statistical power: The power analysis for this study was completed with primary focus on the three hypotheses that comprise Specific Aim 1. We assumed the following race by SES interaction effect sizes for clinical pain severity (Cohen’s $f = .24$), perceived disability (Cohen’s $f = .19$), and functional performance difficulty (Cohen’s $f = .21$) derived from our pilot data. Effect size conventions are .10 (small), .25 (medium), and .40 (large). Probability value was set at .05 and the desired power was set at .85. According to these parameters and effect sizes, a total sample size of 240 participants is required to detect all of the race by SES interaction effects hypothesized for Specific Aim 1 (**Table 5**). These 240 participants will be allocated to four groups, such that there will be 60 low SES Blacks, 60 high SES Blacks, 60 low SES Whites, and 60 high SES Whites. Group sizes of 60 will provide greater than 95% power for detecting pair-wise differences while probing interaction effects based upon alpha level set as two-tailed $.05/6$ contrasts = .008 and Cohen’s d ranging from 0.83 to 1.90 (see C.2.1. above). We plan to over-enroll by 10% to accommodate for participant attrition. Therefore, 268 participants will be recruited with the expectation that at least 240 will complete.

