D.6.2. Data analysis: Data analysis will begin with calculating and comparing measures of central tendency (sample mean, sample median) and dispersion (sample variance, interquartile range) for all cLBP outcomes (e.g., PROMIS pain intensity, GCPS, ODI) as well as other study variables (CPM and TS, oxytocin, vitamin D, CRP levels, sleep, Perceived Injustice, Experiences of Discrimination, CES-D, etc.) according to race by SES groups. Confounding variables may include age, sex, pain medication use, engagement in treatments during the 4 week follow up period, and others as appropriate and will be considered as statistical controls.

Specific Aim 1: General Linear Models incorporating a 2x2 factorial design for Analysis of Covariance (ANCOVA) will be used to examine race by SES differences in cLBP outcomes including pain severity, disability, and functional performance. Race will include Blacks and Whites, while the Hollingshead Index will comprise the primary SES measure with participants split into high versus low SES according to previously published work.^{134,135} Significant interaction effects will be probed using pair-wise contrasts with Bonferroni-adjusted alpha levels to examine differences across racial and SES groups, with emphasis on low SES Blacks compared to high SES Whites. Additional

Table 5: Sample sizes needed to detect hypothesized race by SES differences in cLBP severity, perceived disability, and functional performance with $p < .05$ and power = .85.

Effect size (f)	Sample size needed
Clinical pain severity	.24
Perceived disability	.19
Functional performance	.21

analyses will be completed considering other indicators of high and low SES including subjective social status (MacArthur) and neighborhood SES. This will be done to determine which aspects of SES are most relevant to consider when addressing cLBP outcomes.

Specific Aim 2: The hypotheses that comprise this aim suggest that pain-relevant biopsychosocial factors including endogenous pain modulation, biomarkers, sleep, and psychosocial functioning will also differ according to racial and SES groups. These hypotheses will be tested using 2x2 ANCOVAs in the same manner indicated in Specific Aim 1. Significant race by SES interactions will be probed using pair-wise contrasts adjusted for multiple comparisons.

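### The total of 240 does not follow from the printed inputs: disability at f = .19 needs 251 for 85% power, and 240 gives about 83%

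*Combined protocol and SAP*

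**What the plan says.** Section D.6.1 bases the sample size on the three Specific Aim 1 hypotheses. It takes interaction effect sizes from pilot data: Cohen's f of .24 for clinical pain severity, .19 for perceived disability and .21 for functional performance difficulty. On the error rates it says: "Probability value was set at .05 and the desired power was set at .85". From these it concludes that "a total sample size of 240 participants is required to detect all of the race by SES interaction effects hypothesized for Specific Aim 1", in four groups of 60. After an allowance for attrition, "268 participants will be recruited with the expectation that at least 240 will complete". Section D.1.1 gives the same total of 240 completers.

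Table 5 in D.6.2 is captioned "Sample sizes needed to detect hypothesized race by SES differences in cLBP severity, perceived disability, and functional performance" and repeats the three f values. Its sample-size entries cannot be read in the text supplied, and the pilot-data section (C) is not included, so neither could be checked. That is a limit of the text available, not a fault in the plan.

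For the model, D.6.2 says that "General Linear Models incorporating a 2x2 factorial design for Analysis of Covariance (ANCOVA) will be used" for Aim 1. On covariates it says "Confounding variables may include age, sex, pain medication use", among others, without fixing the list.

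**The concern.** D.6.1 presents 240 as the output of the listed effect sizes, alpha and power. A reader who enters those values in the standard calculation does not get 240 for the outcome that sets the total.

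Disability is one of the three hypotheses on which the study was sized. If the disability interaction turns out null, readers will judge that result against a stated power of 85%, while the printed inputs support about 83% with 240 analysed.

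**Working it through.** **Inputs**
- f = .24, .19 and .21; alpha .05; power .85; 240 analysed in four cells of 60 (D.6.1).
- 2x2 ANCOVA, so the race by SES interaction has 1 numerator df (D.6.2, Specific Aim 1).

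**Method.** Noncentral F with df1 = 1, df2 = N − 4 and noncentrality λ = f² × N. The f is treated as already on the scale of the analysis model, and the cells as equal.

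**Attempt to reproduce 240.** At f = .19 and N = 240, λ = .0361 × 240 = 8.664 with df2 = 236, and power is .834. Power first reaches .85 at N = 251 (.8491 at 250, .8505 at 251, .8519 at 252). The normal approximation agrees: (1.960 + 1.036)² / .0361 = 8.978 / .0361 = 248.7.

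| Outcome | f | N for power .85 | λ at 240 | Power at 240 |
|---|---|---|---|---|
| Pain severity | .24 | 158 | 13.824 | .959 |
| Functional performance | .21 | 206 | 10.584 | .900 |
| Perceived disability | .19 | 251 (252 in equal cells) | 8.664 | .834 |

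The gap for disability is 251 − 240 = 11 participants (4.6% of 240), or .850 − .834 = .016 in power.

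**Other settings at f = .19.** Alpha .10 gives 201; power .80 gives 220; 3 numerator df gives 345; taking off 3 or 5 df for covariates still gives 251. None gives 240.

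**Rounding of f.** Values from .185 to .195 print as .19.
- f = .185: N = 265; power at 240 is .814.
- f = .195: N = 239; power at 240 is .853.
- Threshold for .85 at 240: f = .19421. At four decimals, .1942 gives .84997 (N = 241) and .1943 gives .8503 (N = 240).

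So 240 follows only from the top (.195 − .1942) / .010, or about 8%, of the rounding interval.

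**Covariate allowance.** If the pilot f is unadjusted, the R² that lifts .19 to the threshold is 1 − (.19 / .19421)² = .043. With R² = .05 and three covariates, power at 240 is .853.

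**Larger analysed sample.** At f = .19, .85 is reached with 251 of the 268 recruited (251 / 268 = 94%). With all 268, power is .873 (.855 to .889 for f from .185 to .195).

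**Attrition step.** 240 / .90 = 266.7, so recruiting 268 is consistent with 240 completers. The discrepancy lies only in the 240.

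**The case against.** The arithmetic at f = .19 is not in dispute. The case on the other side is that no error has been shown and that little turns on it.

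- **Rounding.** The effect sizes are pilot estimates reported to two decimals, and 240 lies inside the range of N (239 to 265) that rounding allows. This stands as a possible explanation, but only for f from about .1942 up to .195, and the text supplied gives no finer value.
- **Covariates.** The analysis is an ANCOVA, and covariates explaining about 4.3% of residual variance would close the gap. This also stands as a possibility. D.6.1 makes no such allowance, and the text does not say whether the pilot f is already adjusted.
- **Material out of view.** Table 5's sample-size column and the pilot section might settle the matter. That is why the conclusion is confined to the printed inputs.
- **The gap may not arise.** The Oswestry inventory, which "is a low back-specific instrument designed to address perceived disability in 10 areas", and the Graded Chronic Pain Scale are both collected at session 1 (D.2.1). D.6.2 does not limit Aim 1 to completers, so more than 240 may contribute. This stands, but D.1.1 and D.6.1 justify 240 completers, not a larger session 1 sample.
- **Size.** A loss of 1.6 points on one outcome is smaller than the spread in power from rounding alone (.814 to .853). This is right, and it is why the point is minor.

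**Conclusion.** The concern holds as a minor point about the printed derivation. At f = .19, alpha .05 and power .85, the race by SES interaction needs 251 participants (252 in equal cells), and 240 analysed gives power of about .83. Pain severity and functional performance exceed the target at 240.

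The result rests on three assumptions: the disability f is .19 as printed, it is already on the scale of the analysis model, and the four cells are equal. The third is not assured, because recruitment is stratified by the poverty line (D.1.2) while the analysis splits SES by the Hollingshead Index (D.6.2). As an illustration only, assumed cells of 50, 70, 50 and 70 with the same interaction contrast would give power of about .82.

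Confidence is high for the arithmetic at the printed values. It does not extend to whether the original calculation used a different, unrounded f or a covariate allowance.

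**What to change.** In D.6.1, and in Table 5 where it needs to match, do one of the following.

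1. If the pilot record supports it, print the disability f to four decimals (at least .1943), or the covariate R² allowance, that yields 240.
2. Otherwise, replace the statement of the required total with wording such as:

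> With 240 participants analysed (60 per group) and two-sided alpha .05, power for the race by SES interaction is about 96% for pain severity (f = .24), 83% for perceived disability (f = .19) and 90% for functional performance (f = .21), each per outcome.

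If session 1 disability data from participants who later drop out will be analysed, give that N and its power alongside (.85 at 251, .87 at 268).

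The cost is text in one paragraph and one table. Enrolment, design and analysis stay as they are; under option 2, one stated power becomes about 83% instead of 85%.

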D.1.3. Demographic and SES measures: Ethnic and racial group will be determined by participant self-report using the standard Health and Human Services categories. We will recruit adults who report their ethnicity as non-Hispanic and their race as either Black/African American or White/Caucasian. Because racial groups often differ in socioeconomic status (SES),¹⁰³ and lower SES has been associated with increased risk of clinical pain¹⁰⁴ and increased prevalence of cLBP,¹⁰⁵ we will obtain a multidimensional battery of SES measures as part of this study. We will collect objective and subjective assessments of SES and social standing for individuals as well as the neighborhoods in which they live. The participant's self-reported educational attainment, annual household income, and occupational category will be used as an objective indicator of SES per the **Census Bureau Index of SES**.¹⁰⁶ The **Hollingshead Four-Factor Index of SES** will be used to assess four domains including educational attainment, retired/employed status, marital status, and occupational category/prestige.¹⁰⁷ The **MacArthur Scale of Subjective Social Status** will be used to measure participants' perceived social standing.¹⁰⁸ Research incorporating this measure has shown perceived social status to be determined by occupational position, education, household income, satisfaction with standard of living, and feelings of financial security regarding the future.^{108,109} We will match U.S. Census tract data to participants' addresses **to define neighborhood SES**.⁶⁸ Lastly, participants will self-report whether they currently have health insurance as well as quantity and quality of ongoing cLBP management.

D.2. Experimental session 1

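### Does listing pain medication use as a possible confounder leave the race-by-SES analyses aimed at the wrong disparity?

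*Combined protocol and SAP*

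**What the plan says.** - **D.6.2 Data analysis** names the candidate covariates: "Confounding variables may include age, sex, pain medication use, engagement in treatments during the 4 week follow up period, and others as appropriate". They "will be considered as statistical controls". No final set is fixed. The same section opens with a descriptive comparison of all outcomes by race-by-SES group, before any modelling.
- **D.6.2, Specific Aims 1 and 2** use 2x2 ANCOVAs of race by SES, in which "the Hollingshead Index will comprise the primary SES measure".
- **D.1.1 Participants** explains why daily opioid users are kept in the study. Excluding them could hinder recruitment or "otherwise bias our sampling (e.g., only participants with low severity cLBP not receiving opioids". It adds that "both continued use and temporary withdrawal from these medications (should we ask participants to withhold) could affect pain perception", and that "all medications currently being used for pain (e.g., opioids, NSAIDs, SSRIs, etc.) will be recorded and controlled in statistical analyses as needed".
- **D.1.3 Demographic and SES measures** records that "participants will self-report whether they currently have health insurance as well as quantity and quality of ongoing cLBP management".
- **D.5.1 Follow-up component** notes that "racial group differences in follow up data could be attributed to differences in treatments received or in comorbidities since completion of the experimental sessions", and allows statistical control for these factors if needed.

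The public document begins at the Methods and refers back to sections C.2.1 and C.3.2, which it does not contain. What is said here about an unstated target applies to the text available.

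**The concern.** Age and sex cannot result from a person's back pain or access to care. Current medication can. D.1.1 itself associates not receiving opioids with milder pain, which makes medication a marker of the outcome. It also says medication can alter pain perception, which makes it a cause of the outcome. D.1.3 places insurance and pain care among the SES measures, which suggests a pathway from SES to pain. That last step is an inference, because the Hollingshead Index contains neither item.

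Adjusting for a marker or a pathway changes the quantity estimated. If the ANCOVA includes medication, the interaction is no longer the total disparity but something closer to the disparity at equal medication. A reader who is not told which was intended could misread it. With no rule for when adjustment is needed, the choice could also be made after seeing the data.

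**Working it through.** **The plan's own figures.** D.6.1 gives N = 240 in four groups of 60, alpha .05, desired power .85, and f = .24 (pain severity), .21 (functional performance) and .19 (perceived disability). For a 1-df interaction the noncentrality is N × f²:

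| Outcome | f | 240 × f² | Power |
|---|---|---|---|
| Pain severity | .24 | 13.82 | .96 |
| Functional performance | .21 | 10.58 | .90 |
| Perceived disability | .19 | 8.66 | .83 |

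Disability is slightly under .85 before any adjustment. An f of about .194, which rounds to .19, needs 241, so rounding explains the stated 240.

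**Effect of adding medication.** In SD units the interaction contrast is L = 4f, so .96 for f = .24 and .76 for f = .19. The simulation model is:

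- severity s = L × race × SES + N(0,1);
- probability of medication = logistic(c + k(s − L/4) − a × race × SES);
- observed pain y = s − r × medication.

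Here k is the link from severity to medication, r the relief in SD, a the access deficit in the high-pain cell, and c sets prevalence. The documents give none of these, so all are assumptions. With c = 0 about half the sample is medicated.

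1. *Severity drives medication, which has no effect on pain* (r = 0, a = 0, c = 0; k = .5, 1, 1.5, 2.5). For f = .24 the adjusted interaction is .91, .80, .70, .56 against .96, so 5% to 42% smaller; power is .95, .92, .87, .79 against .96. For f = .19 it is .72, .63, .55, .44 against .76; power is .81, .76, .70, .60 against .83.
2. *Severity drives medication, which relieves pain* (f = .24; r = .3 to .9). With k = .5 the change runs from .93 to .91 (2% smaller) to .86 to .91 (6% larger). With k = 1.5 it runs from .89 to .70 (21% smaller) to .74 to .70 (5% smaller). Adjusted power is about .88 or higher.
3. *Unequal access only* (f = .24; k = 0; low-SES Black participants medicated at 38%, 27% or 18% against 50% elsewhere). The total disparity is 1.00 to 1.25 and the adjusted one about .96, so 4% to 23% smaller. Both are correct answers, to different questions.
4. *As 1, but with about 90% medicated* (c raised to 2.2–3.8). D.1.1 expects recruitment mainly from a pain clinic and counts opioids, NSAIDs and SSRIs, so high use is plausible. For f = .24 the adjusted interaction is .94, .89, .83, .77 (2% to 20% smaller) and power stays at .93 or above. For f = .19 power falls from .83 to about .76 at the strongest link.

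If medication is unrelated to race by SES, adjustment leaves the interaction unchanged.

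**Reading the passages together.** The D.5.1 sentence concerns treatment and comorbidity after the experimental sessions, in data that serve Aim 3. Aim 1 outcomes are measured at sessions 1 and 2, so that sentence is weak evidence for a mediator in Aims 1 and 2. For the same reason, treatment during the four follow-up weeks has no sensible place in the Aim 1 model. The D.1.1 remark on controlling medication arises from sensory testing, where a drug can act on the measurement itself.

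**The case for a change.** The strongest reply is that optional adjustment without a rule is itself the problem. In the first setting with f = .19, the adjusted and unadjusted tests disagreed on significance in 5%, 11%, 19% and 29% of simulated trials as the severity link strengthened. If the total is held at f = .19 and 20% or 40% of it runs through medication, the adjusted f is .19 × .8 = .15 or .19 × .6 = .11, and power at 240 is 65% or 42%. Group summaries at the start of D.6.2 show unadjusted differences but give no interaction test.

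Much of this stands. Medication does differ in kind from age and sex, the covariate set is open, and a reader of the results will need to know which model was fitted. It does not show an error in the plan. The 29% again assumes medication without effect on pain and about half the sample medicated. The 65% and 42% assume the mediated share outright. They describe power for a direct effect, which would be the right quantity if a net-of-treatment disparity were intended.

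**Conclusion.** No change to the plan is needed. What is missing is detail: a fixed covariate set and a named target. The text permits medication adjustment and does not require it, so no wrong analysis is prescribed. Making the medication-adjusted model secondary would be a trade-off. The total disparity includes differences due to treatment, while the adjusted one removes them at the risk of conditioning on severity. For sensory-testing outcomes D.1.1 gives good grounds for adjusting. Medication is recorded for everyone, so an analyst can fit and label both models without new data or a different sample size.

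The direction and size of any shift are unknown. For f = .24 the settings span 42% smaller to 6% larger. Adjusted power drops below .85 only when the severity link is strongest, medication gives no relief and about half the sample uses it. Disability has less margin, but its power is .83 before medication enters the model. All of this rests on assumed prevalence, severity link, relief and access.

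### Adjusting for SES only through a high/low Hollingshead split leaves part of any racial SES difference in the race main effect and same-stratum race contrasts; the score itself should also be in the model.

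*Combined protocol and SAP*

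**What the plan says.** Section D.6.2 makes the Hollingshead Index the primary SES measure for Aim 1 and enters it in a 2x2 ANCOVA with "participants split into high versus low SES according to previously published work". The cut point is left to two cited papers. Aim 2 uses the same model. The additional Aim 1 analyses (subjective status, neighbourhood SES) are also framed as high against low. The confounders named are age, sex, pain medication and treatment during follow-up, with an open-ended clause for others; no SES score is among them. Aim 3 uses SES as a moderator, but in separate models for each race, so it gives no direct race-by-continuous-SES test.

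Section D.1.3 gives a reason for measuring SES in several ways: "Because racial groups often differ in socioeconomic status (SES").

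Section D.6.1 powers the study on the interaction: "Probability value was set at .05 and the desired power was set at .85". It assumes pilot-derived f of .24 (pain), .19 (disability) and .21 (function), and states that "a total sample size of 240 participants is required to detect all of the race by SES interaction effects", allocated as 60 per race-by-SES cell. Pair-wise contrasts are planned at .05/6.

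**The concern.** The Hollingshead index is graded, but the model sees only which side of the cut a person is on. Equal cells of 60 balance the number of people in each stratum, not where they lie within it. If Black participants score lower on average, those in the low stratum will tend to lie below White participants in the low stratum, and likewise in the high stratum. Any effect of that remaining SES gap on pain or disability is then read as an effect of race. A published cut point fixes where the split falls, not what remains inside each half.

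The study sets out to separate race from SES, so this bears on how its race findings are interpreted. A second consequence is possible loss of information on the interaction.

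**Working it through.** **1. The plan's own figure.** For a 2x2 interaction, power comes from the noncentral F with 1 and N − 4 df and noncentrality N·f². With N = 240 and f = .19, noncentrality is 240 × .0361 = 8.66 and power is 83.4%. For f = .21 it is 90.0%, and for f = .24 it is 95.9%. Exactly f = .19 needs N = 251 for .85, but an unrounded f of .1945 gives 240. The stated sample size therefore reproduces within rounding, as a calculation for the 2x2.

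**2. SES gap left within strata.** Assume a normal score with SD 1 in each race, means D apart, and a cut midway. By the truncated-normal mean, the gap inside either stratum is

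g = D − φ(D/2)·[1/(1 − Φ(D/2)) − 1/Φ(D/2)].

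For D = 0.8: 0.8 − 0.3683 × (2.902 − 1.526) = 0.293, or 37% of D. For D = 0.3, g = 0.109, or 36%. For small D the share tends to 1 − 2/π = 36%.

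**3. Effect on race tests.** Assume a linear SES effect with correlation r, no true race effect, and 60 per cell. The spurious race difference is r·g.

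- *D = 0.8, r = .5:* the difference is .5 × 0.293 = 0.147 SD. The score's variance within a stratum is about 0.37, so the outcome SD within a cell is √(0.75 + 0.25 × 0.37) = 0.918. The SE of the race main effect is 0.918 × 2/√240 = 0.118, and the ratio 1.24 gives rejection in about 23% of trials. For a same-stratum contrast the SE is 0.918 × √(2/60) = 0.168, and the ratio 0.87 gives about 4% at .05/6.
- *D = 0.3, r = .3:* the difference is 0.033 SD. The SEs are 0.125 and 0.177, and rejection is about 6% and 1%.

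Simulation (4,000 runs per row) agrees:

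| Race gap D | r | Race main effect, split | Interaction, split | Race, continuous score |
|---|---|---|---|---|
| 0.3 | .3 | 5.5% | 5.4% | 4.7% |
| 0.3 | .5 | 7.0% | 4.5% | 4.4% |
| 0.5 | .3 | 6.8% | 5.3% | 4.8% |
| 0.5 | .5 | 11.9% | 5.1% | 5.3% |
| 0.8 | .3 | 11.0% | 5.1% | 5.1% |
| 0.8 | .5 | 23.0% | 4.6% | 5.1% |

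Separate simulations put the last race figure between 22% and 24%. Adding the continuous score to the 2x2 as a covariate also returns the race test to about 5%.

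**4. An off-centre cut.** If the cut is placed to match the poverty rates in section D.1.2 (13% and 31%, used only as an illustration), the implied gap is 0.63 SD, with 0.14 SD left in the low stratum and 0.36 SD in the high. False race effects are then 9% to 18%, and false interactions 6% to 8%.

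**5. Information on the interaction.** For a linear effect, a median split of a normal score keeps 2/π = 64% of the information, so f shrinks by √0.637 = 0.798.

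- *If the pilot f describes the continuous effect:* f on the split is .19 × 0.798 = .152, noncentrality is 5.52, and power is 65% against 83% with the score. For function the split has 73%, and for pain 84%.
- *If the pilot f came from split groups:* f on the score is .19/0.798 = .238, and power rises from 83% to about 96% with the score. For function it rises from 90% to 98%, and for pain from 96% to over 99%.
- *If the effect is a step at the cut:* the order reverses. At f = .19, simulation gives 82% for the split and 63% for the score.

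**The case against.** The strongest reply is that the inflation affects a test the plan does not feature. Aim 1 is powered on the interaction, which keeps its 5% level under a central cut. Pair-wise contrasts follow only a significant interaction and use .05/6. Along that path, for gaps of 0.6 to 0.8 SD, either same-stratum race contrast is falsely declared in only 1.2% to 2.3% of runs. The contrast the plan emphasises, low-SES Black against high-SES White participants, combines race and SES on purpose. All of this stands, and it limits the size of the problem. It does not remove it: the 2x2 model yields a race main effect, nothing says it will go uninterpreted, and Aim 2 hypothesises differences by racial group in the same model.

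The second reply is that the inputs are assumed. The documents give no Hollingshead distribution by race, no SES-outcome correlation and no cut point. That also stands: at a 0.3 SD gap the error rate is only about 6% to 7%.

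Third, the power loss depends on the shape of the SES effect, which the documents do not give. A linear continuous model could lose as much as it gains.

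The extra SES measures and the open-ended covariate clause help a little, but neither commits the analysis to the Hollingshead score.

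**Conclusion.** The point holds for the race main effect and for same-stratum race contrasts. With a roughly normal score and a central cut, about 36% of any race difference in SES stays within strata. Under gaps of 0.3 to 0.8 SD and correlations of .3 to .5, both assumed, the main-effect error rate is about 6% to 23% instead of 5%. Contrasts at .05/6 falsely reject in about 1% to 4% of runs instead of 0.8%.

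A reader might infer three stronger things that the documents do not support:

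- *That the powered interaction test is invalid.* It stays near 5% with a central cut, and reaches only 6% to 8% with the off-centre cut tried here.
- *That the study misses its .85 power.* The calculation is for the 2x2 and gives 83.4% at f = .19. If the pilot values came from split groups, any loss is already included. The plan does not say which scale they are on.
- *That the 2x2 must be replaced.* It matches the four-group design used for the power calculation, and under a step effect it is the better test. Adding the score is enough to correct the race comparison.

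**What to change.** 1. Keep the 2x2 cells for recruitment and display, and write the Hollingshead cut point into the plan.
2. Add the continuous Hollingshead score as a covariate in the 2x2 ANCOVA for Aims 1 and 2. This alone returns the race test to about 5%. The SES main effect in that model is then no longer the plain high-low difference, so report the unadjusted cell means beside it.
3. Prespecify a race-by-continuous-Hollingshead model and report race differences at a low and a high score. Check linearity with something flexible such as a spline; a quadratic detects a symmetric step poorly.
4. State in section D.6.1 whether the pilot f values are on the split or the continuous scale.

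Cost: SAP wording and one more model per outcome, using a score already collected. The downsides are a functional-form assumption to check and results less simple than four cell means.
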